9.5.4.5 Breaking the Blind

Not applicable.

9.5.4.6 Regulatory Reporting of Adverse Events

AEs will be reported by the Sponsor or a third party acting on behalf of the Sponsor to regulatory authorities in compliance with local and regional law and established guidance. The format of these reports will be dictated by the local and regional requirements.

All studies that are conducted within any European country will comply with European GCP Directive 2005/28/EC and Clinical Trial Directive 2001/20/EC. All SUSARs will be reported, as required, to the competent authorities of all involved European member states.

9.5.5 Completion/Discontinuation of Subjects

The investigator may discontinue study drug for a subject at any time for safety or administrative reasons. A subject may elect to discontinue study drug and study participation at any time for any reason. All subjects who discontinue study drug are to complete the Off-Treatment visit, as indicated in the Schedule of Procedures/Assessments [Table 6](#) and [Table 7](#).

Study drug is to be discontinued for the following reasons:

- Progression of disease that, in the opinion of the investigator, precludes further study treatment. (After consultation with the Sponsor, H3B-6527 may be continued for a subject who has met the criteria for PD but, in the investigator's opinion, is receiving benefit.)
- Occurrence of an unacceptable AE.
- Subjects who do not receive study drug for at least 17 of 21 days (approximately 80%, not necessarily consecutively) during the first cycle for reasons not considered to be a DLT by both the investigators and the Sponsor will be replaced. The subjects who are replaced will not be considered evaluable for DLT assessments.
- Subject requires use of a prohibited concomitant medication or therapy.
- General or specific changes in the subject's condition unacceptable for further treatment within the study parameters, in the judgment of the investigator.
- Non-compliance.
- Lost to follow-up.
- Subject, investigator, or Sponsor request.

The reason for study drug discontinuation is to be documented in the CRF.

Subjects who discontinue study drug for reasons other than PD are to continue to have tumor measurements and disease response assessments performed every 6 weeks until the development of PD. After development of PD, subjects who discontinue study treatment, regardless of their reasons for doing so, will be followed for survival approximately every 12 weeks for up to 12 months or until 6 cycles after last patient in, death, loss to follow-up, or withdrawal of consent, whichever occurs first. However, subjects may continue to receive study treatment, as long as they demonstrate clinical benefit as judged by the investigator after discussion with the Sponsor or until the end of the study.

Study participation also may be discontinued for any of the following reasons:

- Subject withdrawal of consent
- Non-compliance
- Lost to follow-up
- Sponsor request
- Closure of the study by the Sponsor.

The reason for study discontinuation is to be documented in the CRF.

The investigator will promptly explain to the subject involved that the study will be discontinued for that subject and provide appropriate medical treatment and other necessary measures for the subject. A subject who has ceased to return for visits will be followed by mail, telephone, or other means to gather information such as the reason for failure to return, the status of treatment compliance, the presence or absence of AEs, and clinical courses of signs and symptoms.

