9.3.2 Exclusion Criteria

Subjects who meet any of the following criteria will be excluded from this study:

1. Other malignancy active within the previous 2 years except for basal or squamous cell skin cancer, stage 1 prostate cancer, superficial bladder cancer, or carcinoma in situ of the cervix or breast that has completed curative therapy.
2. Current evidence of corneal disorder/keratopathy including but not limited to corneal epithelial thinning, bullous/band keratopathy, corneal abrasion, inflammation/ulceration, or keratoconjunctivitis (to be confirmed by ophthalmological examination). Pre-existing cataract is not a reason for exclusion.
3. Brain or subdural metastases are not eligible, unless they have completed local therapy and have discontinued the use of corticosteroids for this indication for at least 4 weeks before starting treatment in this study. Any signs (eg, radiologic) or symptoms of brain metastases must be stable for at least 4 weeks before starting study treatment.
4. Genetic diseases of the liver that may complicate review of safety data.
5. Known human immunodeficiency virus infection.
6. Uncontrolled significant active infections, except HBV or HCV. Subjects with HBV are eligible, but should be taking appropriate antiviral medication if indicated. Subjects with HCV are eligible but must not be taking any concomitant treatment for HCV while receiving H3B-6527.
7. Major surgery or other locoregional treatment within 4 weeks before the first dose of study drug or radionuclide treatment (eg, ⁹⁰Yttrium intra-arterial treatment) within 8 weeks before the first dose of drug administration.
8. Inability to take oral medication, or presence of malabsorption syndrome or any other uncontrolled gastrointestinal condition (eg, nausea, diarrhea, or vomiting) that might impair the bioavailability of H3B-6527. Subjects with prior gastric resection are eligible.
9. Use of any drug that is a strong inhibitor or inducer of the CYP3A4 enzyme or the P-glycoprotein transporter within at least 2 weeks before the start of study drug and during the conduct of the study unless there is an emergent or life-threatening medical condition that requires it.
10. Use of any drug known to prolong corrected QT (QTc) interval within at least 2 weeks before the start of the study drug and during the conduct of the study.

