9.4.2 Guidelines for Continuation of Treatment

Study drug should continue to be administered as planned unless a DLT has occurred. Subjects who experience a DLT during C1 will be discontinued from treatment. In rare cases, an exemption to study discontinuation for a DLT in 1st cycle may be considered after discussion between the treating physician, Sponsor and study medical monitor. If a subject should experience a DLT or DME (ie, an AE meeting the criteria for a DLT but occurring after C1) during the study then study treatment will be interrupted and subjects may, at the discretion of the investigator, and after discussion with the Sponsor, be allowed to continue study drug at a reduced dose, if the following criteria are met:

- ANC $\geq 1.0 \times 10^9/L$ (1,000/mm³)
- Platelet count $\geq 75 \times 10^9/L$ (75,000/mm³)
- All other nonhematologic treatment-related toxicities are Grade 0 or 1 (except alopecia) or return to baseline level
- Clinical benefit is being received, and
- Evidence of an otherwise favorable risk/benefit profile.

The magnitude of the dose reduction cannot be specified *a priori* since the actual doses evaluated and the dose-toxicity relationship will not be known until there is clinical experience with H3B-6527; however, a minimum reduction of 33% must be taken. The dose chosen will require discussion and agreement between the investigator and Sponsor following review of the relevant clinical data.

Dose reductions are allowed for all subjects. However, once the H3B-6527 dose has been reduced for a given subject, no re-escalation will be permitted for that subject.

A maximum of 2 dose reductions will be allowed as needed, but study treatment should not be resumed in the case of the following treatment-related events:

- Occurrence of a DLT in C1 except upon agreement with investigator, Sponsor and medical monitor. A dose reduction must be taken if treatment is resumed.
- CTCAE Grade 3 or 4 cardiac event
- Nonhematologic events of Grade 4 severity
- Dose delay of ≥ 21 days for a treatment-related event in C2 and beyond.

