9.4.8.1 Prohibited Concomitant Therapy and Procedures

The following therapies and procedures are prohibited during study participation:

- Other investigational drugs.
- Other antitumor therapies such as chemotherapy, surgical resection, or antitumor immunotherapy.
- Proton pump inhibitors.
- Radiotherapy for central metastases (eg, vertebral, mediastinal) will not be allowed; the need for such radiotherapy while on study will be seen as an indication of disease progression and the subject should be withdrawn from therapy. However, palliative radiotherapy for up to 2 local peripheral metastases not being used as target lesions is allowed but the need for such therapy may be an indication of PD and should be discussed with the Sponsor prior to implementation.
- Drugs that are strong inhibitors or inducers of CYP3A4 enzyme (see list in Table 4) or P-glycoprotein transporter.
- Drugs that raise serum calcium and phosphorus levels (eg, vitamin D supplements, calcium dietary supplements, calcium antacids) or systemic corticosteroids. The duration between the last systemic corticosteroid administration and the first dose of study drug should be at least 2 weeks. If a short-term course of systemic corticosteroids is required while on treatment, then study drug must be held while the subject receives systemic corticosteroid treatment. If the subject has not progressed in the interim, resumption of treatment with H3B-6527 may be considered following discontinuation of steroid treatment and a 2-week washout period.

Table 4 Inducers and Strong Inhibitors of CYP3A4

INDUCERS
Carbamazepine, efavirenz, nevirapine, phenobarbital, phenytoin, pioglitazone, rifabutin, rifampin, St. John's Wort, troglitazone
STRONG INHIBITORS
Indinavir, nelfinavir, ritonavir, clarithromycin, itraconazole, ketoconazole, nefazodone

Source: [Indiana University Department of Medicine. <http://medicine.iupui.edu/clinpharm/ddis/clinical-table>](http://medicine.iupui.edu/clinpharm/ddis/clinical-table) Accessed September 7, 2016

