Management of hyperphosphatemia or hypercalcemia: Phosphorus and calcium will be measured at screening, before the first dose, every week with safety labs during C1, and on Day 1 and Day 8 for C2 and beyond. Please note that a treatment cycle is 21 days. Subjects with elevated levels of phosphorus or calcium at screening, as defined as being over the ULN on local lab ranges, may not participate in this study and should be referred for management of such. If successfully controlled, subjects may be rescreened. During study participation, any confirmed levels of phosphorus above 7 mg/dL, or calcium equal to or above Grade 2 hypercalcemia as per CTCAE, Version 4.03, will result in the dose of H3B-6527 being held for 14 days. The hyperphosphatemia and / or hypercalcemia should be managed by local practice, with medication, diet change and potential referral as necessary. After 14 days of holding the drug, if the phosphorus level has returned to 5.5 mg/dL or lower, and the calcium is less than or equal to a Grade 1 elevation, the subject may begin taking H3B-6527 again at one dose level lower than their original dose and should continue other measures initiated during the drug holiday, such as phosphorus lowering agents, while on study. If a subject should experience hyperphosphatemia above 7 mg/dL or hypercalcemia equal to or above Grade 2 again on study, then study therapy will be discontinued.

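### Protocol 9.5.5 lists need of any prohibited drug, and fewer than 17 dosed days in Cycle 1, as reasons to stop study drug, in conflict with the hold-and-possible-restart rules in 9.4.8.1 and 9.4.8.2

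*Protocol*

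**What the plan says.** The list in Protocol 9.5.5 is introduced by "Study drug is to be discontinued for the following reasons". Two of its items matter here.

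- The first is "Subject requires use of a prohibited concomitant medication or therapy", with no qualification or cross-reference.
- The second begins "Subjects who do not receive study drug for at least 17 of 21 days (approximately 80%, not necessarily consecutively) during the first cycle" and continues "for reasons not considered to be a DLT by both the investigators and the Sponsor will be replaced". It adds that replaced subjects are not DLT-evaluable.

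Other sections deal with the same situations differently.

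- **Corticosteroids.** Section 9.4.8.1, repeated in the synopsis under concomitant therapy, puts systemic corticosteroids on the prohibited list. If a short course is needed on treatment, study drug must be held. If there has been no progression, "resumption of treatment with H3B-6527 may be considered following discontinuation of steroid treatment and a 2-week washout period".
- **Strong CYP3A4 or P-glycoprotein drugs.** Exclusion criterion 9 (9.3.2 and synopsis) covers use before and during the study "unless there is an emergent or life-threatening medical condition that requires it". Section 9.4.8.1 and the synopsis list of prohibited therapy bar the same classes with no such exception.
- **Phosphorus and calcium.** Section 9.4.8.2, and the matching synopsis text, require a 14-day hold above stated limits. If the values have recovered to stated levels by then, "the subject may begin taking H3B-6527 again at one dose level lower than their original dose".
- **The 17-of-21-day sentence.** It also appears in the synopsis (dose escalation), Protocol 9.4.4.1 and 9.7.1.8, and SAP 5.6. In all four it decides only replacement and DLT evaluability. Protocol 9.1.1.1.1 confines DLTs to Cycle 1 of Phase 1, and SAP 5.2.1 confines the DLT Analysis Set to Part 1.

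**The concern.** A site that reads 9.5.5 first and a site that reads 9.4.8 first could treat the same event differently, one stopping study drug for good and the other holding it and possibly restarting. Both would be following the protocol.

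The split would reach the data. Disposition tables count discontinuations by primary reason (Protocol 9.7.1.3, SAP 5.2.2). Duration of treatment and dose intensity (SAP 5.6.1) depend on whether the subject resumes, and so does the time available to respond.

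In Part 2 the second item would apply a sentence written for DLT evaluability where no DLT can occur. Because it speaks of replacement, it also leaves open who counts toward the 40 evaluable subjects per schedule in Protocol 9.7.2.

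**Working it through.** **Inputs.** Cycle length is 21 days (9.4.1). The threshold is 17 dosed days (9.5.5). The mineral hold is 14 days (9.4.8.2). The corticosteroid hold is the course plus a 14-day washout (9.4.8.1).

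**1. The plan's own figure.** 17/21 = 0.8095, which agrees with the stated approximate 80%. At most 21 − 17 = 4 days may be missed.

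**2. Prohibited medication, side by side.** No arithmetic is needed.

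| Situation | 9.5.5 | Other section |
|---|---|---|
| Short systemic corticosteroid course | Discontinue | 9.4.8.1: hold; resumption may be considered after washout |
| Strong CYP3A4/P-glycoprotein drug in an emergency | Discontinue, since 9.4.8.1 prohibits it | Exclusion 9: excepted |
| Radiotherapy to central metastases | Discontinue | 9.4.8.1: withdraw from therapy (agrees) |

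The first row is a direct conflict. In the second, an exception stands in one place and is missing from the other two. The third shows that the conflict does not extend to everything on the prohibited list.

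**3. Cycle 1 dosed days under a hold.** Let the first missed dose be on Day s and the hold last H days, with every other day dosed. Then

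dosed days = 21 − min(H, 22 − s).

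For the mineral hold, H = 14:

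| Start day s | Dosed days | Below 17? |
|---|---|---|
| 1 to 8 | 21 − 14 = 7 | yes |
| 9 | 21 − 13 = 8 | yes |
| 15 | 21 − 7 = 14 | yes |
| 17 | 21 − 5 = 16 | yes |
| 18 | 21 − 4 = 17 | no |

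Every start from Day 1 to Day 17 falls short, and none from Day 18 on does. A corticosteroid hold with an assumed one-day course (H = 15) leaves 6 days if it starts by Day 7 and 14 if it starts on Day 15. It too reaches 17 only from Day 18.

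**4. Visit windows.** The Cycle 1 visits are Day 8 ± 3 and Day 15 ± 3. If the hold starts on the visit day, a Day 5 to 11 start leaves 7 to 10 dosed days, and a Day 12 to 18 start leaves 11 to 17. Only the last day of the second window escapes.

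**5. Which rule then applies.** The 9.5.5 item covers only reasons not considered a DLT.

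- *Part 1.* Table 2 lets a related Grade 2 nonhematologic toxicity that prevents 17 days of dosing be deemed dose-limiting by agreement. A Grade 3 or higher event may also qualify. The subject then leaves the 9.5.5 item and comes under the Cycle 1 DLT provisions of 9.4.2. If the event is not deemed a DLT, the 9.5.5 item applies.
- *Part 2.* There are no DLTs, so any such Cycle 1 hold falls under the 9.5.5 item as written.

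**The case against.** The strongest reply is that the 17-of-21-day sentence is simply in the wrong place. The item speaks of replacement, not discontinuation, its content is about DLT evaluability, and everywhere else it is only that. A sensible site may see this, and may also let the specific corticosteroid rule override the general item. This stands as a guess at intent. The heading still says discontinue, however, and 9.5.5 neither refers to 9.4.8 nor limits the item to Part 1.

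It is also fair that both restarts are permissive. Only the holds are mandatory, so 9.4.8 does not oblige a site to restart. The conflict is between stopping and being allowed to resume.

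A reader might infer a further contradiction with 9.4.2, which lists "Dose delay of ≥ 21 days for a treatment-related event in C2 and beyond" among the cases where treatment should not be resumed. An assumed 7-day corticosteroid course plus the 14-day washout gives 7 + 14 = 21 days, which would meet that limit while 9.4.8.1 lets resumption be considered. The documents do not support calling this a contradiction. A permission and a limit on it can both be followed, 9.4.8.1 gives no course length, and whether the washout counts as delay for a treatment-related event is not stated. At most it is a point to clarify.

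**Conclusion.** The conflict holds on two points. The prohibited-medication item in 9.5.5 contradicts the corticosteroid hold in 9.4.8.1, and the emergency exception in exclusion 9 has no counterpart in 9.4.8.1. The 17-of-21-day item, read under its heading, discontinues a subject with a non-DLT mineral hold starting on Cycle 1 Day 1 to 17, while 9.4.8.2 permits restart once values have recovered.

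Three wider readings should be avoided. Not every Cycle 1 hold is caught, since starts from Day 18 leave at least 17 dosed days. Hold-and-resume is not offered for prohibited drugs in general; among them it covers only systemic corticosteroids. The enrolment ceiling of 128 is not a count of affected subjects; the documents give no frequency.

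The day counts assume continuous daily dosing with no other missed days. The hold is counted from the first missed dose, which may be later than the blood sample, because 9.4.8.2 requires a confirmed phosphorus level. The Part 2 conclusion takes Phase 1 and Phase 2 in 9.1.1.1.1 to mean Parts 1 and 2.

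**What to change.** Reconcile 9.5.5 with 9.4.8.1, 9.4.8.2 and exclusion criterion 9, and with the matching synopsis text, so that each situation has one rule. The clinical rule in each case is for the sponsor to choose.

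- For prohibited medication, make the 9.5.5 item, the corticosteroid text and the emergency exception say the same thing, by cross-reference or by removing whichever text does not apply.
- For the 17-of-21-day sentence, state whether it is a replacement and evaluability rule for Part 1 only or a reason to discontinue, and whether it applies in Part 2. State also how it relates to the 14-day mineral hold.
- As a clarification, say how a corticosteroid hold plus washout counts toward the 21-day delay limit in 9.4.2.

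The cost is protocol wording in an amendment or clarification letter, with no added procedures or subjects.

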9.5.6 Abuse or Diversion of Study Drug

Not applicable.

9.5.7 Confirmation of Medical Care by Another Physician

The investigator will instruct subjects to inform site personnel when they are planning to receive medical care by another physician. At each visit, the investigator will ask the subject whether he/she has received medical care by another physician since the last visit or is planning to do so in the future. When the subject is going to receive medical care by another physician, the investigator, with the consent of the subject, will inform the other physician that the subject is participating in the clinical study.

9.6 Data Quality Assurance

This study will be organized, performed, and reported in compliance with the protocol, Standard Operating Procedures, working practice documents, and applicable regulations and guidelines. Site audits may be made periodically by the Sponsor's or the CRO's qualified compliance auditing team, which is an independent function from the study team responsible for conduct of the study.

9.6.1 Data Collection

Data required by the protocol will be collected on the CRFs and entered into a validated data management system that is compliant with all regulatory requirements. As defined by ICH guidelines, the CRF is a printed, optical, or electronic document designed to record all of the protocol-required information to be reported to the Sponsor on each study subject.

Data collection on the CRF must follow the instructions described in the CRF Completion Guidelines. The investigator has ultimate responsibility for the collection and reporting of all

clinical data entered on the CRF. The investigator or designee as identified on Form FDA 1572 must sign the completed CRF to attest to its accuracy, authenticity, and completeness.

Completed, original CRFs are the sole property of H3 Biomedicine and should not be made available in any form to third parties without written permission from H3 Biomedicine, except for authorized representatives of H3 Biomedicine or appropriate regulatory authorities.

9.6.2 Clinical Data Management

All software applications used in the collection of data will be properly validated following standard computer system validation that is compliant with all regulatory requirements. All data, both CRF and external data (eg, laboratory data), will be entered into a clinical system.

9.7 Statistical Methods

All statistical analyses will be performed by the Sponsor or designee after the study is completed and the database is locked and released. Statistical analyses will be performed using WinNonlin and SAS software or other validated statistical software as required. Details of the statistical analyses will be included in a separate statistical analysis plan.

9.7.1 Statistical and Analytical Plans

The statistical analyses of study data are described in this section. Further details of the analytical plan will be provided in the statistical analysis plan, which will be finalized before database lock.

9.7.1.1 Study Endpoints

The primary study endpoints are:

- Occurrence of DLTs as a function of the dose of H3B-6527 for determination of the MTD and RP2D.
- Safety/tolerability: the type and frequency of AEs, SAEs using CTCAE, Version 4.03, as well as changes in clinical laboratory values, ECG parameters, and vital sign measurements.

Secondary study endpoints are:

- PK: standard primary PK parameters including, but not limited to, the area under the plasma concentration-time curve from time 0 through the last measurable point (AUC_{0-t}), maximum observed plasma concentration (C_{max}) and time of maximum observed plasma concentration (t_{max}).
- Preliminary antitumor activity: Response will be determined by the investigator using mRECIST ([Appendix 1](#)). The following endpoints will be determined:

- ORR, defined as the proportion of subjects achieving a best overall confirmed response of partial response (PR) or CR (PR + CR), from first dose date until disease progression/recurrence.
- Duration of response, defined as the time from the date of first documented CR/PR until the first documentation of disease progression as determined by the investigator or death, whichever comes first.
- Progression-free survival (PFS), defined as the time from first dose date to the date of the first documentation of disease progression as determined by the investigator or death (whichever occurs first).
- Overall survival (OS), defined as the time from first dose date to the date of death.
- Time to response, defined as the time from first dose date to the date of first documented CR/PR.

Exploratory study endpoints include:

- Correlation of biomarker expression levels with antitumor activity and safety
- Expression levels of biomarkers in blood and tumor samples
- Correlation of biomarker expression levels with H3B-6527 exposure in plasma
- H3B-6527 levels in tumor tissue may be assessed
- H3B-6527 metabolites in plasma and urine

